7.5. Day 8 (Phone Call)

The following procedures and assessments will be performed by phone call on Day 8:

- AE recording
- Concomitant medication recording
- Instruction on how to administer study drug

7.6. Visit 5; Day 15

The following procedures and assessments will be performed at Visit 5:

- Collect and dispense study drug
- Collect and dispense subject diary
- Blood sample collection for PK analysis
- AE recording
- Concomitant medication recording
- LTS scoring
- Instruction on how to administer study drug
- Study drug administration under supervision

7.7. Day 22 (Phone Call)

The following procedures and assessments will be performed by phone call on Day 22:

- AE recording
- Concomitant medication recording
- Instruction on how to administer study drug

7.8. Visit 6; Day 29

The following procedures and assessments will be performed at Visit 6:

- PGA score
- %BSA affected calculation (performed before PASI); subject's scalp, palms, and soles should be excluded from the %BSA calculations
- PASI
- Continuous Holter Monitoring for 13 hours (1 hour prior to dosing and 12 hours post-dose)
- Collect subject diary
- Blood and urine sample collection for clinical laboratory tests
- Blood sample collection for PK analysis and
- AE recording
- Concomitant medication recording
- LTS scoring
- Study drug administration under supervision
- Collect study drug

7.9. Visit 7; Day 30

The following procedures and assessments will be performed at Visit 7:

- Continuous Holter Monitoring for 1 hour (1 hour prior to PK sample collection)
- Blood sample collection for PK analysis and
- AE recording
- Concomitant medication recording

7.10. Visit 8; Follow-Up (7-10 days After Day 29)/Early Termination

Follow-up/Early Termination assessments are as follows:

- ECG recording
- Urine pregnancy test (WOCBP only)
- Brief physical examination
- Vital signs measurements
- Blood and urine sample collection for clinical laboratory tests
- AE recording
- Concomitant medication recording

8. SAFETY MONITORING AND REPORTING

8.1. Adverse Events, Treatment-Emergent Adverse Events, Serious Adverse Events, and Adverse Events of Special Interest

The Investigator or site staff is responsible for detecting, documenting and reporting events that meet the definition of an AE, TEAE, SAE, or adverse event of special interest (AESI). At each visit/contact, subjects should be questioned in a general way so as not to introduce bias in detecting AEs, TEAEs, and/or SAEs. Open-ended and non-leading verbal questioning of the subject is the preferred method to inquire about AE and TEAE occurrence.

Investigators are not obligated to actively seek AEs, TEAEs, or SAEs in former study subjects. However, if the Investigator learns of any SAE, including a death, at any time after a subject has been discharged from the study, and he/she considers the event reasonably related to the study drug or study participation, the Investigator should promptly notify the Sponsor.

8.1.1. Definition of Adverse Events

An AE is any untoward medical occurrence in a subject temporally associated with the use of a study drug, whether considered causally related or not related to the study drug.

An AE can therefore be any unfavorable and unintended sign (including an abnormal laboratory finding), symptom, or disease (new or exacerbated) temporally associated with the use of a study drug.

Events meeting the definition of an AE include:

- Any abnormal laboratory test results (e.g., hematology, clinical chemistry) or other safety assessments (e.g., vital signs measurements), including those that worsen from Baseline, and felt to be clinically significant in the medical and scientific judgment of the Investigator;
- Exacerbation of a chronic or intermittent pre-existing condition (e.g., atopic dermatitis) including either an increase in frequency and/or intensity of the condition;
 - For skin-related AEs, it should be noted whether or not the event is in the area of active application of study drug, and/or if spreading beyond the application site.
- New conditions detected or diagnosed after study drug administration even though it may have been present prior to the start of the study;
- Signs, symptoms, or the clinical sequelae of a suspected interaction;
- Signs, symptoms, or the clinical sequelae of a suspected overdose of either study drug or a concomitant medication (overdose per se will not be reported as an AE/SAE);
- "Lack of efficacy" or "failure of expected pharmacological action" per se will not be reported as an AE or SAE. However, the signs, symptoms, and/or clinical sequelae resulting from lack of efficacy will be reported as AE or SAE if they fulfill the definition of an AE or SAE.
- Evaluation of local tolerability at the site of topical application (e.g., burning/stinging, pruritus, and erythema).

Events that **do not** meet the definition of an AE include:

- Any clinically significant abnormal laboratory findings or other abnormal safety assessments that are associated with the underlying disease, unless judged by the Investigator to be more severe than expected for the subject's condition;
- The disease/disorder being studied or expected progression, signs, or symptoms of the disease/disorder being studied, unless more severe than expected for the subject's condition:
- Medical or surgical procedure (e.g., endoscopy, appendectomy); the condition that leads to the procedure is an AE.
- Situations where an untoward medical occurrence did not occur (social and/or convenience admission to a hospital);
- Anticipated day-to-day fluctuations of pre-existing disease(s) or condition(s) present or detected at the start of the study that do not worsen.

8.1.2. Definition of Treatment-Emergent Adverse Event

A TEAE is an AE that occurs following the first application of study drug.

8.1.3. Definition of Serious Adverse Event

If an event is not an AE per Section 8.1.1 or a TEAE per Section 8.1.2, then it cannot be an SAE even if serious conditions are met (e.g., hospitalization for signs/symptoms of the disease under study, death due to progression of disease, etc.).

An SAE is any untoward medical occurrence that, at any dose:

- Results in death;
- Is life-threatening refers to an event in which the subject was at risk of death at the time of the event. It does not refer to an event, which hypothetically might have caused death, if it were more severe.
- Requires hospitalization or prolongation of existing hospitalization;
 - In general, signifies that the subject has been detained (usually involving at least an overnight stay) at the hospital or emergency ward for observation and/or treatment that would not have been appropriate in the physician's office or outpatient setting. Complications that occur during hospitalization are AEs. If a complication prolongs hospitalization or fulfills any other serious criteria, the event is serious. When in doubt as to whether "hospitalization" occurred or was necessary, the AE should be considered serious.
 - Hospitalization for elective treatment of a pre-existing condition that did not worsen from Baseline is not considered an AE.
- Results in disability/incapacity: a substantial disruption of a person's ability to conduct normal life functions;
 - This definition is not intended to include experiences of relatively minor medical significance such as uncomplicated headache, nausea, vomiting, diarrhea,

influenza, and accidental trauma (e.g., sprained ankle) which may interfere or prevent everyday life functions but do not constitute a substantial disruption.

- Results in a congenital anomaly/birth defect;
- Medical or scientific judgment should be exercised in deciding whether reporting is appropriate in other situations, such as important medical events that may not be immediately life-threatening or result in death or hospitalization but may jeopardize the subject or may require medical or surgical intervention to prevent one of the other outcomes listed in the above definition. These should also be considered serious. Examples of such events are invasive or malignant cancers, intensive treatment in an emergency room or at home for allergic bronchospasm, blood dyscrasias or convulsions that do not result in hospitalization, or development of drug dependency or drug abuse.

8.1.4. Adverse Events of Special Interest

In prior clinical studies, the following AEs have been identified as AEs of particular clinical importance and will be reported as AESIs in this study; in each case study drug may be discontinued, based upon Investigator's judgment, and the subject may be discontinued from the study.

- Contact dermatitis: the study site should collect location, duration, size, associated symptoms (itching, burning, pain), severity (mild, moderate, or severe), and photograph the affected site (if possible). If subject contacts the study site to report significant skin irritation at or near the site of study drug application between study visits, the subject should be brought for an unscheduled visit, if possible.
- Folliculitis: the study site should collect the location, duration, size, associated symptoms (itching, burning, pain), severity (mild, moderate, or severe), indicate whether pustular, and photograph the affected site (if possible).
- Headache: site should collect duration, severity (mild, moderate, or severe), onset, and location.

For each AESI, a narrative may be written and included in the Clinical Study Report.

8.2. Classification of Adverse Events

8.2.1. Assigning Severity Rating for Adverse Events

8.2.1.1. Criteria for Determining Adverse Event Severity

The Investigator will make an assessment of the severity of each AE and SAE according to the National Cancer Institute Common Terminology Criteria for Adverse Events (CTCAE), v. 5.0, 2017. For terms not specified with the CTCAE, the criteria in Table 5 should be used to determine the grade severity.

Table 5: Criteria for Determining the Grade/Severity of Adverse Event Terms Not Specified by the National Cancer Institute CTCAE

Grade	Criteria
1	Mild; asymptomatic or mild symptoms, clinical or diagnostic observations only; intervention not indicated
2	Moderate; minimal, local, or noninvasive intervention indicated; limiting age-appropriate instrumental activities of daily living ^a
3	Severe or medically significant but not immediately life-threatening; hospitalization or prolongation of hospitalization indicated; disabling; limiting self-care activities of daily living ^b
4	Life-threatening consequences; urgent intervention indicated
5	Death related to AE

Abbreviation: AE = adverse event; CTCAE = Common Terminology Criteria for Adverse Events

AE severity should be recorded in the appropriate section of the eCRF and in the subject's source documents.

8.2.1.2. Toxicity Management Criteria

8.2.1.2.1. Grade 1 or Grade 2 Adverse Event

Subjects who develop a Grade 1 or Grade 2 AE may continue study drug at the discretion of the Investigator. Subjects who choose to withdraw from study due to a Grade 1 or 2 AE should have early termination assessments completed as outlined in Section 7.10.

8.2.1.2.2. Grade 3 Adverse Event

Subjects who develop a Grade 3 AE should be managed as follows:

- If the Investigator has compelling evidence that the Grade 3AE has not been caused by study drug, then dosing may continue after discussion with the Medical Monitor.
- Subjects who develop a Grade 3 AE that the Investigator considers related to study drug should have the study drug discontinued. Subjects experiencing Grade 3 AEs requiring permanent discontinuation of study drug should be followed weekly until resolution or stability of the AE and encouraged to have early termination assessments completed as outlined in Section 7.10.

8.2.1.2.3. Grade 4 Adverse Event

Subjects who develop a Grade 4 AE should have study drug permanently discontinued.

Subjects experiencing Grade 4 AEs requiring permanent discontinuation of study drug should be followed weekly until resolution or stability of the AE and encouraged to have early termination assessments completed as outlined in Section 7.10.

^a Instrumental activities of daily living refer to preparing meals, shopping for groceries or clothes, using the telephone, managing money, etc.

^b Self-care activities of daily living refer to bathing, dressing and undressing, feeding self, using the toilet, taking medications, and not bedridden.

8.2.1.2.4. Other Management Criteria

The Medical Monitor should be notified if any of the following occur:

• Severe signs or symptoms, or significant changes in any of the safety assessments, that put the safety of the subject at risk (e.g., laboratory tests or vital signs, etc.) as judged by the Investigator.

8.2.2. Assigning Causal Relationship to Study Drug

The Investigator is to make the causality assessment. Causality assessment is not to be delegated; however, if delegation is unavoidable due to Investigator inaccessibility, this must be recorded as a protocol deviation. The reasonable possibility of the relationship of an AE to study drug is to be assessed with careful medical consideration at the time of evaluation of an AE. The following definitions are to be used for the relationship of the AE to study drug:

- **Related**: A clinical event, including laboratory test abnormality, with a temporal relationship to study drug administration that makes a causal relationship plausible, unlikely attributed to concurrent disease or other drugs or chemicals, and that follows a clinically reasonable response on re-administration (rechallenge) or withdrawal (dechallenge), although information on drug withdrawal may be lacking or unclear.
- **Not related**: A clinical event, including laboratory test abnormality, with a temporal relationship to study drug administration that makes a causal relationship improbable and/or in which other drugs, chemicals, or underlying disease provide a plausible explanation.

Any AEs /SAEs assessed as related to study participation (e.g., protocol-mandated procedures, invasive tests, or change in existing therapy) or related to study drug will be recorded from the time a subject consented to participate in the study up to and including any follow-up contact.

All AEs, whether related to study drug or not, must be fully and completely documented on the AE page of the eCRF and in the subject's clinical record. In the event a subject is withdrawn from the study because of an AE, the primary reason for withdrawal (i.e., due to an AE) must be recorded on the eCRF as such.

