1. INTRODUCTION

1.1. Background Information and Study Rationale

1.1.1. Background Information

Psoriasis is a common, chronic relapsing inflammatory skin disease [Parisi, 2012] with recurrent episodes of prominently erythematous and scaly patches (plaques). Approximately 2 to 3% of the global population is affected by psoriasis; those affected are predominantly adults, who are most often diagnosed between the ages of 18 to 35 years. Psoriasis disrupts daily activities such as work attendance, interpersonal relationships, recreational activities, and intimacy, thereby significantly impacting sufferers' quality of life. Furthermore, psoriasis sufferers can also have co-morbidities such as arthritis, depression, inflammatory bowel disease, and CV diseases.

Up to 80% of patients have mild to moderate plaque-type psoriasis, which is generally managed with topical treatments. The most commonly used treatments for psoriasis include topical corticosteroids and Vitamin D analogs, alone or in combination. Vitamin D analogs are moderately efficacious as monotherapy, whereas application of topical corticosteroids, particularly the very potent ones, is restricted in terms of body areas that can be treated and the duration of use due to the well-known application site and systemic adverse drug reactions [Mason, 2013]. Although numerous topical treatment options are available, there remains a need for a topical treatment that combines a high level of efficacy with an acceptable safety profile and permits application to a large body surface area (BSA) without restrictions on duration of treatment.

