1.3.1. Risk Assessment

1.3.1.1. Dermatological Adverse Events, Including Skin Irritation, or Allergic Reaction:

Tapinarof or its excipients may induce skin irritation. Allergic or irritant reactions in the exposed areas may present as erythema, edema, papules, or vesicles. In the event of pronounced skin reaction, spreading of the eczematous reaction beyond the original application site(s) and/or more generalized (remote) skin reactions may be observed.

In the dose-ranging study (Study 203120) in subjects with psoriasis, the most frequently reported dermatologic AEs were folliculitis and contact dermatitis. In the dose-ranging study (Study 203121) in subjects with atopic dermatitis, the most frequently reported dermatologic AEs were folliculitis and atopic dermatitis. Nonclinical dermal toxicity studies of up to 8% tapinarof for up to 13 weeks indicated local effects are primarily mild-to-moderate skin irritation that is reversible; tapinarof did not show evidence of sensitization. In initial clinical studies using a different formulation of tapinarof AEs of skin hyperpigmentation, application site dermatitis, papular rash, pruritus, contact dermatitis, folliculitis, erythema, and skin burning sensation were reported.

1.3.1.2. Systemic Adverse Events:

Nasopharyngitis and headache were the most frequently reported nondermatological AEs in the dose-ranging study (Study 203120) in subjects with psoriasis. In the dose-ranging study (Study 203121) in subjects with atopic dermatitis, the most frequently reported nondermatological AEs were nasopharyngitis, upper respiratory tract infection, and headache. In the initial clinical studies (in psoriasis and atopic dermatitis) using a different tapinarof formulation, nasopharyngitis, and headache were the most frequently-reported nondermatological AEs. In Study 201851 with of tapinarof cream, 1% and 2%, headache was most frequently reported during the study (reported for 100% and 60% of subjects at the 1% and 2% doses, respectively).

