8.5. Pregnancy Management and Reporting

Any female subject who becomes pregnant during the study will be withdrawn. Details will be collected for all pregnancies in female subjects that begin after the start of dosing and through the Follow-up visit. Pregnancy is not automatically considered an AE.

If a pregnancy is reported, then the Investigator should complete a pregnancy data collection form and submit via email or fax to the Pregnancy Reporting Contact for which contact information can be found on the Medical Monitor/Sponsor Information Page of this protocol, within 2 weeks of learning of the pregnancy. The subject will also be followed to determine the outcome of the pregnancy. Information on the status of the mother and child will be forwarded to the Sponsor. Generally, follow-up will be no longer than 6 to 8 weeks following the estimated delivery date. Any premature termination of the pregnancy will be reported.

Any SAE occurring in association with a pregnancy brought to the Investigator's attention after the subject has completed the study and considered by the Investigator as possibly related to the study drug must be promptly reported to the Sponsor or the Sponsor's representative.

The Investigator must attempt to collect pregnancy information on any female partners of male study subjects who become pregnant while the subject is enrolled in the study. Pregnancy information must be reported to the Sponsor or the Sponsor's representative as described above. The partner will also be followed to determine the outcome of the pregnancy. Information on the status of the mother and child will be forwarded to Sponsor or the Sponsor's representative. Generally, follow-up will be no longer than 6 to 8 weeks following the estimated delivery date. Any premature termination of the pregnancy will be reported on the pregnancy report form.

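### Read literally, Protocol 8.2.2 classes an adverse event with two plausible causes as not related, so the treatment-related TEAE summaries could under-count

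*Protocol*

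**What the plan says.** Protocol 8.2.2 opens with a standard: "The reasonable possibility of the relationship of an AE to study drug is to be assessed with careful medical consideration at the time of evaluation". It does not define that standard further. It then makes two categories binding: "The following definitions are to be used for the relationship of the AE to study drug".

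- *Related* needs a timing that makes a drug cause plausible, and an event "unlikely attributed to concurrent disease or other drugs or chemicals". It also refers to the response to rechallenge or withdrawal, but allows that withdrawal information may be missing.
- *Not related* covers an event whose timing "makes a causal relationship improbable and/or in which other drugs, chemicals, or underlying disease provide a plausible explanation".

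There is no intermediate category.

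The call is then used in two ways.

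- **Summaries.** Protocol 10.4.2 plans a summary of TEAEs that the Investigator considers related. SAP 10.4 adds a two-way split by relationship, SAP 12 adds drug-related AEs overall and by maximum severity, and SAP Appendix C lists the tables.
- **Stops.** Two of the four mandatory reasons to stop study drug in Protocol 4.6.1 depend on relatedness.

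**The concern.** The lead-in asks whether a drug cause is reasonably possible. The definitions ask, in effect, whether the drug is the only plausible cause. These are different questions, and they give different answers when both the cream and something else could explain the event.

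Such events are foreseeable in this trial. Protocol 1.3.1.1 says of the cream: "Allergic or irritant reactions in the exposed areas may present as erythema, edema, papules, or vesicles". Protocol 1.1.1 describes psoriasis plaques as erythematous too. Headache is an AESI, reported by all subjects on the 1% cream in an earlier atopic dermatitis study, and it is a symptom for which a non-drug explanation can often be offered.

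Every subject receives tapinarof, open label, with no vehicle arm (Protocol 3.2, 5.2 and 5.3). Within the AE tables, the Investigator's causality call is therefore the main means of separating drug effect from background. Safety is a primary objective, and Protocol 1.1.2 says the results are meant to support US registration. A reader of the study report would naturally take the related-AE rate as a reasonable-possibility rate. If Investigators at the approximately six sites resolve the wording differently, the calls could also vary between sites.

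**Working it through.** The plan gives no figure to reproduce. The check applies the wording to every combination of causes and then traces where the result is used.

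**Step 1. Apply both standards.**

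| Drug cause plausible | Other cause plausible | Definitions in 8.2.2, read literally | Reasonable possibility, ordinary reading |
|---|---|---|---|
| yes | no | Related | Related |
| yes | yes | Not related | Related |
| no | yes | Not related | Not related |
| no | no | Not related | Not related |

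The definitions put one of the four cells under *Related*; the ordinary reading of the lead-in puts two there. They differ only in the second row. That event fails the condition that another cause be unlikely, and it meets the second limb of *Not related*, which the and/or makes sufficient alone. Measured against the lead-in, the wording can move events only out of *Related*.

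**Step 2. Look for a repair elsewhere.** SAP 10.4 counts a missing relationship as related. That reaches blank fields only, not events recorded as not related. No other rule in either document reclassifies them.

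**Step 3. Count the tables affected (SAP Appendix C).**

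- Four TEAE tables (14.3.2.1.1 to 14.3.2.1.4), three treatment-related tables, and 14.3.3.1 and 14.3.3.2: 4 + 3 + 2 = 9.
- Omit a two-cause event: the three treatment-related tables, 3 of 9.
- Keep it but show it as not related: 14.3.2.1.4 and 14.3.3.2, 2 of 9. The second is touched only by events that lead to discontinuation. SAP 10.4 classifies each subject by the closest relationship, so in 14.3.2.1.4 the event matters only if the subject has no related event at the same level.
- No relationship in the title: 9 − 3 − 2 = 4. The overall summary 14.3.2.1.1 may still carry a relationship line.

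This counts where one field is used. It does not measure bias.

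**Step 4. Trace the stops.**

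- Grade 4: 8.2.1.2.3 stops study drug whatever the cause.
- Grade 3: 8.2.1.2.2 lets dosing continue with compelling evidence that study drug was not the cause, after discussion with the Medical Monitor. Two plausible causes do not amount to that. One seam remains: a Grade 3 event called *Not related* without compelling evidence fits neither bullet of 8.2.1.2.2.
- Below Grade 3: the related-and-severe-enough reason in 4.6.1 applies only when the Investigator already thinks stopping is warranted, and 4.6 lets the same Investigator stop for safety at any time.

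**Step 5. Scale.** Neither document gives a frequency for events with two plausible causes. For scale only, one subject of approximately 20 is 1/20 = 5 percentage points of incidence. This is not an estimate of the shift.

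**The case against.** The strongest reply is that the protocol leaves reasonable possibility undefined and gives the definitions in the same paragraph, so they may simply be how it puts the phrase into practice. There would then be no second standard to fall short of. Wording elsewhere does not settle this. Protocol 8.1 asks for notice of an SAE learned of after discharge when "he/she considers the event reasonably related to the study drug or study participation, the Investigator should promptly notify the Sponsor". Protocol 8.5 covers a post-study pregnancy-associated SAE "considered by the Investigator as possibly related to the study drug must be promptly reported to the Sponsor". Both are reporting triggers, and the first is not clearly wider than *Related*. An Investigator might also treat the definitions as guides to judgement, and the eCRF completion guidance, which could resolve the matter, is not among the documents reviewed. This is why the summaries *could* under-count, not that they will. It does not remove the literal result for two-cause events, or the likelihood that a reader will take the rate in its ordinary sense.

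The erythema example is narrower than it looks. Protocol 8.1.1 excludes expected signs of psoriasis from AEs, so the example applies only to reactions more severe than expected or recorded as local tolerability events. A reader might infer that ordinary plaque redness is being miscounted; the documents do not support that. Irritation is also captured without any causality call by the LTS at Baseline and Days 15 and 29, and contact dermatitis, folliculitis and headache have their own listings.

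A reader might also infer that the mandatory stops are materially weakened, since two of the four use relatedness. Read with 4.6 and 8.2.1.2, the protocol does not support that. The effect is nil for Grade 4 and small otherwise.

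**Conclusion.** The point holds for the treatment-related summaries. Read literally, the definitions class an event with two plausible causes as *Not related*. Against the ordinary meaning of reasonable possibility, the shift can only be downward. Its size is unknown.

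Unaffected are the AE frequency and severity endpoint, the all-TEAE tables, LTS scores, AESI listings, on-study SAE reporting (which 8.4.1 requires whatever the relationship) and Grade 4 stops. No formal safety comparison is planned (Protocol 10.4.2). The documents therefore do not support a conclusion that the primary safety evaluation is biased or that subjects lose a meaningful protection.

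The conclusion assumes that Investigators apply the definitions as written and that no unseen eCRF guidance overrides them. It is a low-priority correction, but more than a missing detail, because it concerns a stated rule.

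**What to change.** In Protocol 8.2.2, define *Related* as a reasonable possibility that study drug caused the event, even if another cause is also plausible. Define *Not related* as no reasonable possibility that study drug caused it. Issue matching eCRF guidance.

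Apply the new pair prospectively, because 8.2.2 places the assessment when the event is evaluated. Re-assessing earlier events should not be the default: it adds Investigator work and invites hindsight reclassification in an open-label study. If it is done before database lock, keep the original call on record. If it is too late to amend, state in the study report that relatedness calls used the narrower definition.

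Optionally, align the Grade 3 wording in 4.6.1 with the compelling-evidence test in 8.2.1.2.2, and state there that without such evidence study drug stops. This closes the seam noted above.

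The cost is a short amendment with IRB/IEC approval under 11.1.2, the eCRF guidance, and a related-AE rate that may be slightly higher. The study-report sentence costs almost nothing.
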